#### 6.4.4 Vital Signs

The following vital signs will be measured:

- Blood pressure (supine) (systolic and diastolic [mmHg])
- Orthostatic blood pressure (systolic and diastolic [mmHg])
- Heart rate (bpm)
- Body temperature (°C) (oral, tympanic, temporal, or forehead infrared)
- Respiratory rate (breaths per minute)

Supine BP and HR recordings will be made after the subject has been supine for at least 5 minutes. The assessment will be performed as per Appendix 2 Schedule of Assessment. The first blood pressure will be the average of 3 measurements recorded after the subject is supine for 5 minutes; the second blood pressure will be recorded after the subject has stood for up to 3 minutes. A drop in blood pressure of  $\geq$  20 mmHg, or in diastolic blood pressure of  $\geq$  10 mmHg will be considered abnormal.

#### 6.4.5 Weight

Additionally, weight (kg) and BMI (kg/m^2) will be measured under the same Vital sign assessment.

#### 6.4.6 12-Lead Electrocardiogram

The 12-lead ECGs will be performed after the subject has been resting supine for ≥ 5 minutes. The assessment will be performed as per Appendix 2 Schedule of Assessment. The ECG will include all 12 standard leads and a Lead II rhythm strip on the bottom of the tracing. The following ECG parameters will be collected: PR interval, QRS interval, RR interval, QT interval, mean heart rate, QTcB and QTcF interval.

All ECGs must be evaluated by the investigator or qualified designee for the presence of abnormalities. Collection and analysis of ECG data will be performed by a central ECG vendor.

Confidential Page 26 of 57

#### 6.4.7 Physical and Neurological Examination

The physical examination includes an assessment of general appearance and a review of systems (dermatologic, head, eyes, ears, nose, mouth/throat/neck, thyroid, lymph nodes, respiratory, cardiovascular, gastrointestinal, extremities, musculoskeletal, neurologic, and psychiatric systems).

Neurological components include, but are not limited to, the following assessments: mental status, cranial nerves, muscle strength, tone, and bulk, reflexes, coordination, sensory function, and gait.

The assessment will be performed as per Appendix 2 Schedule of Assessment.

#### 6.4.8 Columbia-Suicide Severity Rating Scale (C-SSRS)

The C-SSRS supports suicide risk assessment through a series of simple, plain-language questions. The responses assist in identifying whether a subject is at risk for suicide, assesses the severity and immediacy of that risk, and gauge the level of support that the subject may require. The assessment will be performed as per Appendix 2 Schedule of Assessment.

#### 6.4.9 Geriatric Depression Scale (GDS)

The GDS is a self-report measure of depression in older adults with a "Yes/No" response format; The GDS was originally developed as a 30-item instrument. It has since been validated in a shortened form comprising 15 items (Sheikh and Yesavage, 1986). The total score range is 0 to 15, with a higher score indicating more severity. The assessment will be performed as per Appendix 2 Schedule of Assessment.

#### 6.6 Genotyping

Blood sample(s) will be collected at Screening for analysis of GBA genotype in subjects who consented to genotyping.

Confidential Page 27 of 57

Confidential Page 28 of 57

#### 7 STUDY POPULATIONS

## 7.1 Analysis Populations

## 7.1.1 Intent-to-Treat (ITT) Population

The ITT population will consist of all randomized subjects regardless of whether or not the subject received test article. A subject is considered randomized when the IxRS provides the test article assignment (ie, completes a randomization transaction). Subjects will be analyzed according to the dose they were randomized to.

## 7.1.2 Modified Intent-to-Treat (mITT) Population

The modified intent-to-treat (mITT) population will include all randomized subjects who took at least one dose of the study medication and who completed both an ADAS-Cog13 and ERP P300 assessment at Baseline and during at least one post-baseline visit. Subjects will be analyzed according to the dose they were randomized to.

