#### **Statistical Methods:**

### General Statistical Methods and Types of Analysis:

Clinical effect analyses will be based on the modified intent-to-treat (MITT) Population, consisting of all randomized subjects who took at least one dose of the study medication and who completed both an ADAS-Cog13 score and ERP P300 latency assessment during Baseline and at least one post-baseline visit.

The primary clinical effect endpoint is the GST (combining the ADAS-Cog13 score and the ERP P300 latency) change from baseline at Week 26 relative to the placebo group. The primary analysis will use a mixed model for repeated measures (MMRM) with change from baseline as the outcome variable, and terms for baseline, baseline by time interaction, and baseline by time by treatment interaction in the model. Additional terms will be included for GBA genotype, and site (with smaller sites grouped). Least squares means and treatment differences will be estimated from the MMRM model.

An interim analysis of the ERP-P300 and safety data is planned when at least 30 subjects have completed the Week 2 visit.

Safety analyses will be based on the Safety Population consisting of all randomized subjects who received at least one dose of the study medication. All safety parameters will be summarized descriptively.

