# 6.3 Pharmacodynamic Variables

Pharmacodynamic variables will consist of ERP P300 assessments. ERP P300 should be performed when the subject is not experiencing interfering motor disturbances that might affect the quality of ERP P300 data; if necessary, the time window for ERP P300 assessments can be extended.

ERP P300 is a method of recording brain activity elicited by external stimuli, e.g., an oddball auditory stimulus, and is a well-established functional biomarker, particularly of working memory access (Ally, 2006). ERP P300 is characterized by a stereotyped series of voltage deflections occurring after the respective odd tone to be counted, with early features (< 100 msec) corresponding to unconscious sensory transmission (auditory cortex, N100), and later features produced by cognitive processing in the ventral attentional network, i.e., P300, referring to the large positive deflection at roughly 300 msec in healthy adults (young or elderly). The P300 latency is sensitive to detecting reduced synaptic transmission related to cognitive decline in AD patients and other dementias (Olichney, 2011).

To assess the P300 wave (latency and amplitude), the subject is in a semi-sitting position, eyes closed, and has to perform a task related to auditory stimuli. The stimulus consists of an oddball paradigm with 2 sound stimuli. Stimuli are presented through headphones and auditory stimulation for P300 will be assessed in a recording lasting up to 10 minutes.

ERP P300 will be performed at the Pre-baseline visit (Visit 2a, Day -10 to Day -3, no dosing). ERP P300 data should be uploaded for quality check immediately after the completion of the Pre-baseline visit (Visit 2a).

At Baseline/Day 1 (Visit 2b), ERP P300 will be performed at pre-dose following the completion of baseline assessments of ADAS-Cog13, and up to 1.5 hour before dose in clinic. EEG will be assessed post-dose at approximately 2 (±1) hours after IMP dosing.

At Visits 3, 5, and 8, ERP P300 will be performed at pre-dose up to 1 hour before dose in clinic. ERP P300 will be assessed post-dose following the completion of ADAS-Cog13, assessments, at approximately 2 (±1) hours after IMP dosing.

ERP P300 will also be performed at the Safety follow-up visit (Visit 9, no dosing).

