# 10.5 Efficacy

Summary statistics will include change from baseline comparison of ATH-1017 with placebo using a two-sample t-test without baseline adjustment. All statistical tests will be carried out using a one-sided 2.5% significance level and all comparisons will be reported with 95% confidence intervals for mITT population unless otherwise stated. The comparison between ATH-1017 (40 mg and 70 mg pooled) and placebo will serve as the primary efficacy comparison. This summary will be produced for each disease type and AChEI usage within disease type also.

Confidential Page 35 of 57

No adjustments will be made for multiple comparisons.

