## 10.5.2 Secondary Analysis

NOTE: The following description for the secondary analyses was prepared to implement the intention of the protocol, however in view of the early stopping of the trial this analysis will not be performed, unless the simple summary statistics suggest a finding of interest, in which case these would be performed as exploratory analysis.

The separate key secondary variables ADAS-Cog13 and ERP P300 latency will be analyzed using the MMRM model. Change form baseline ADAS-Cog13 score and change form baseline ERP P300 latency will be used as the outcome variable and the following fixed terms: baseline value, treatment arm, visit, treatment by visit interaction, baseline by visit by treatment interaction, GBA genotype, and baseline age. in the MMRM model. Similar summary statistics will be presented that was used for analysis of the primary endpoint. If MMRM model do not converge, active treatment and placebo groups will be compared using one sided t-test 2.5% significance level at Week 26 for change for baseline secondary variables.

Confidential Page 37 of 57

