# **Appendix 4.** Summary of Efficacy Analyses

**Table 6.** Analyses of Efficacy Parameters

Parameter	Population	Statistical Method	Missing Data	Interpretation	Table Number
GST Score	mITT	t-test/MMRM	NA	Primary analysis	Table 14.2.3.1
CFB ADAS- Cog13 score	mITT	t-test/MMRM	NA	Secondary analysis	Table 14.2.3.2
CFB ERP P300 latency	mITT	t-test/MMRM	NA	Secondary analysis	Table 14.2.3.3

mITT = Modified intent-to-treat; MMRM = Mixed Model Repeated Measures; CFB = change from baseline

Confidential Page 52 of 57

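### The mITT rule requiring both ADAS-Cog13 and P300 is also applied to the separate analyses of each, so observed data on one endpoint are discarded when the other is missing

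*SAP*

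**What the plan says.** **Entry rule.** SAP 7.1.2 limits mITT to "all randomized subjects who took at least one dose of the study medication and who completed both an ADAS-Cog" score and a P300 recording. The data condition in full is "completed both an ADAS-Cog 13 and ERP P300 assessment at Baseline and during at least one post-baseline visit". Protocol 8.1.1 has the same rule.

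**Where it applies.** The protocol synopsis states: "Clinical effect analyses will be based on the modified intent-to-treat (MITT) Population". SAP 10.5 makes this the default for efficacy: "all comparisons will be reported with 95% confidence intervals for mITT population unless otherwise stated". Table 6 in SAP Appendix 4 names mITT for the GST score and for both components. The ADAS-Cog13 row reads "CFB ADAS- Cog13 score mITT t-test/MMRM NA Secondary analysis".

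**The component analyses.** The secondary objective (Protocol 2, SAP 5.2) is to evaluate cognition and P300 latency separately. SAP 10.5.2 says: "The separate key secondary variables ADAS-Cog13 and ERP P300 latency will be analyzed using the MMRM model". It names no other population.

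**ITT.** SAP 7.1.1 defines a wider set: "The ITT population will consist of all randomized subjects regardless of whether or not the subject received test article". No analysis in the visible text is assigned to it.

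**Status.** The trial stopped early. SAP 6 calls efficacy exploratory, and SAP 8 rules out statistical conclusions. The mITT t-test summaries in 10.5 still run. Under 10.5.1 and 10.5.2 the MMRMs run only if those summaries show something of interest.

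**The concern.** A rule that both components be present follows from what the GST is: without both there is no score. It has no such basis when ADAS-Cog13 or P300 is analysed alone. There, a missing value on one endpoint removes observed values on the other before any model sees them. An MMRM can use subjects with incomplete follow-up, but not subjects whom the population flag has already taken out.

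Two things are at stake. The first is precision in a trial planned at 75 and stopped short of that. The second is selection: the post-baseline half of the rule depends on what happens after randomization, so the arms compared on cognition are filtered by whether a P300 recording was completed later. The same holds for P300, filtered by ADAS-Cog13.

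The t-test summaries also decide whether an MMRM is run, so the population affects that decision as well as the estimates.

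**Working it through.** **1. Which set each analysis uses**

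| Analysis | Needs | Set in Table 6 |
|---|---|---|
| GST score | both components | mITT (both required) |
| Change in ADAS-Cog13 | ADAS-Cog13 only | mITT (both required) |
| Change in P300 latency | P300 only | mITT (both required) |

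The rule matches the need in the first row only.

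**2. Who is excluded.** ADAS-Cog13 is scheduled at Baseline and Weeks 2, 12, 20 and 26. P300 is scheduled at Visit 2a, at Visit 2b, before and after dosing at Weeks 2, 12 and 26, and at Week 30 (Protocol Table 1, SAP Appendix 2). The P300 condition removes a subject from the ADAS-Cog13 analysis only if there was no completed P300 at Baseline, or none at any post-baseline visit.

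**3. The plan's own figure.** SAP 6.1.2 gives 25 per arm: 3 × 25 = 75, which checks. It rests on no formal calculation, so there is no effect size, SD or power to reproduce.

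**4. Ceiling on the loss.** Inputs from the documents: 75 subjects allocated 1:1:1, pooled active against placebo (50 against 25), one-sided 2.5% level. Assumed: a share *f* is excluded, equal across arms, and every excluded subject would otherwise have contributed in full.

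- Standard error factor = 1/√(1 − *f*)
- Detectable difference at 80% power = (1.960 + 0.842) × √(1/n_placebo + 1/n_active)
- With none excluded: 2.802 × √(1/25 + 1/50) = 2.802 × 0.2449 = 0.69 SD
- Power at an assumed true effect of 0.7 SD = Φ(0.7/0.2449 − 1.960) = Φ(0.898) = 81.5%

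| *f* (assumed) | Left of 75 | Standard error factor | Detectable difference | Power at 0.7 SD |
|---|---|---|---|---|
| 0 | 75 | 1.000 | 0.69 SD | 81.5% |
| 5% | 71.25 | 1.026 | 0.70 SD | 79.5% |
| 10% | 67.5 | 1.054 | 0.72 SD | 77.4% |
| 20% | 60 | 1.118 | 0.77 SD | 72.4% |
| 30% | 52.5 | 1.195 | 0.82 SD | 66.7% |

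The standard error factor does not depend on the total enrolled. The other columns use the planned 75, which the trial did not reach.

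**5. Why this is a ceiling.** Let *g* be the share of excluded subjects who have an ADAS-Cog13 value at the visit analysed. If all included subjects have one, the factor becomes √(1 + *fg*/(1 − *f*)). At *g* = 1 this is 1/√(1 − *f*), as in the table; at *g* = 0 nothing is lost. The two measures share the Week 2, 12 and 26 visits, so a subject with no post-baseline P300 will often have left early and have no Week 26 ADAS-Cog13 either. That puts *g* below 1.

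**6. Small cells.** SAP 9.1 also presents efficacy by disease type, AChEI use and treatment group. At the planned size that is 75/(2 × 2 × 3), or about 6 subjects per cell, so a single avoidable exclusion shows.

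**The case against.** **One set for all three is defensible.** It lets a reader set the components against the composite in the same subjects, the protocol prespecified it, and the SAP follows the protocol. This is a real advantage. It supports showing components in the joint set as a secondary display. It does not justify discarding valid data when the stated aim is to evaluate each component separately.

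**The exclusion may be rare.** A reader might infer that one failed EEG removes a subject. The documents do not say so: the criterion is a completed assessment at Baseline and at one or more later visits, not a usable one and not one at Week 26. Visit 2a has an immediate quality check, and Protocol 7.4.2 asks early leavers to return for the Week 26 assessments. This stands, and it lowers the likely size.

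**The excluded subjects may not be sicker.** Protocol 6.3 says "ERP P300 should be performed when the subject is not experiencing interfering motor disturbances that might affect the quality of ERP P300 data", and a reader might infer that failures concentrate in more impaired subjects. The same sentence goes on to allow a wider time window, so it is a mitigation. Neither document links failed recordings to cognitive severity. Selection is possible, but its direction is unknown.

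**ITT.** A reader might infer that the ITT set is never used. That can be checked only in the visible text: SAP 10.5.3, 10.5.4 and the exploratory endpoints are not shown, and the randomized count in 10.1 is the ITT count without the name. An unused definition changes no result.

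**Efficacy is exploratory.** This is correct and limits the consequence. The t-test summaries still run on this set, however.

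**Conclusion.** The point holds as a mismatch between population and analysis. SAP 10.5 and Table 6 carry the joint rule into two analyses that need only one component each, so observed data are lost and avoidable selection on a post-randomization event is added.

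The size cannot be read from the documents. If 5% to 30% were excluded, equally across arms, about 4 to 22 of the planned 75 subjects would go, and the standard error of the component comparison would rise by at most about 3% to 20%. The true figure is probably lower, since many of those excluded would have had little ADAS-Cog13 follow-up to lose. No stated number in the plan is wrong, and no bias in a particular direction has been shown.

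The change is worth making because it costs almost nothing and affects summaries that will still be produced. With efficacy exploratory, its practical effect is modest.

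**What to change.** - Keep the joint mITT set for the GST.
- In SAP 10.5, 10.5.2 and Table 6, analyse each component in all randomized and dosed subjects, by randomized arm, who have a baseline and at least one post-baseline value of that component. Apply this to the t-test summaries and to any MMRM.
- In 7.1.2, say whether an unreadable recording counts as completed, and whether both measures must come from the same post-baseline visit.
- Note the change in SAP 8, since the protocol assigns mITT to all clinical effect analyses.

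The new sets should not be labelled ITT. They require a dose and data on the endpoint, so they differ from SAP 7.1.1. They still condition on a post-baseline value of the endpoint analysed, so they reduce post-randomization selection without removing it.

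Cost: a sentence or two, one population flag per component, and slightly different denominators between the GST and its components. No new data are needed.

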#### 7.1.3 Per Protocol (PP) Population

The per protocol population will include all mITT subjects who were medication compliant during the 26 weeks of double-blind treatment, completed both an ADAS-Cog13 and ERP P300 assessment during at least one post-baseline visit, and did not have any major protocol deviations. Subjects will be analysed based on actual treatment received.

All criteria for subject removal from PP are identified and confirmed prior to data base lock.

#### 7.1.4 Safety Population

The Safety population will include all randomized subjects who received at least one dose of the study medication. Subjects will be analyzed based on actual treatment received.

Confidential Page 29 of 57

# 8 CHANGES IN CONDUCT OR PLANNED ANALYSES FROM THE PROTOCOL

The following changes have been made in the analytical strategies:

Since the study is stopped early, minimal analyses will be performed.

- No interim analysis will be performed.
- Alternate statistical comparison tests can be implemented as appropriate.
- No statistical conclusion can be made based on the statistical test, if generated.
- Other than summary statistics, all exploratory and subgroup analysis are optional.

Confidential Page 30 of 57

#### 9 OVERALL STATISTICAL CONSIDERATIONS

#### 9.1 General Conventions

Efficacy and safety data will be summarized and presented by disease type (PDD or DLB), acetylcholinesterase inhibitor (AChEI) usage within disease type, treatment group, and time point in summary tables. Continuous variables will be presented by descriptive statistics: n, mean, standard deviation (SD), median, minimum, and maximum. Categorical variables will be tabulated by frequency count and percentage. Percentages are based on the number of subjects in each treatment group in the given population for AE summary tables, and additionally overall for medical history, prior and concomitant medications. For all other tables, percentages are based on the number of subjects with non-missing data in each treatment group and overall for the given population.

Means, medians and percentiles will be displayed to one more decimal place than the data, dispersion statistics (e.g., standard deviation) will have two more decimal places, and the minimum and maximum will be displayed to the same number of decimal places as reported in the raw data. Percentages will be displayed with one decimal place. P-values will be quoted to 4 decimal places consistent with SAS PVALUEw.d format set to PVALUE6.4. P-values < 0.0001 will be presented as p<0.0001.

Listings will include all subjects with defined analysis population for each listing. Listings will generally be sorted by disease type, treatment, subject ID, parameter and visit date/study day. Unscheduled visits will also be included in the listings.

Days will be converted to weeks by dividing by seven. Days will be converted to months by dividing by 30.44. Days will be converted to years by dividing by 365.25. All data collected during the study will be analyzed and reported except as stated otherwise.

All data will be analyzed using the SAS® Version 9.4 or later.

#### 9.2 Baseline Definition

For safety summaries, the last pre-randomization measurement is defined as the baseline value. For clinical effect measures baseline is defined as the last pre-randomization measurement.

GST score, ADCS-CGI-C, and CaGI-C are change scores, so no further calculation is required. Appendix 1 describes calculation of the baseline GST score for baseline covariate purposes. For all other efficacy measures, baseline is the average of all measurements prior to first dosing, or if only one measurement exists that value will be used.

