# 3.1 Justification for Study Design

The study is designed as a safety and proof of concept study of ATH-1017 in PDD and DLB subjects using a double-blind, placebo-controlled, parallel-arm treatment duration of 26 weeks. The target population is based on clinical diagnostic criteria of PDD (Emre, 2007) or DLB (McKeith, 2017) in combination with severity assessments and the inclusion/exclusion criteria.

Any rational assessment of cognitive change can only be performed using a double-blind, placebo-controlled, randomized study design. A study duration of 26 weeks is in keeping with the rivastigmine trial (Emre, 2004) that led to US FDA approval for the use of rivastigmine in PDD subjects.

Clinical effects in the target patient population are assessed by improvement in cognition and global as well as functional variables comparing treatment to placebo. The GST combines the endpoints ADAS-Cog13 (i.e., cognition) and change in ERP P300 latency into a single primary endpoint, allowing an unbiased assessment of the overall treatment effects of ATH-1017 in this complex disorder. The inclusion of an additional assessment of ERP P300 at a pre-Baseline visit in addition to corresponding baseline assessments pre-dose at the Baseline/ Day 1 visit of the study is intended to reduce possible variability of the baseline measure for this functional variable.

As well as providing pharmacodynamic data on the effect of ATH-1017 on ERP P300 latency in this patient population, this study will provide data on clinical effects using validated outcome scales for cognitive function, executive memory function, activities of daily living, motor function, and behavioral changes.

The safety assessments for the study are generally accepted measures for ensuring safety of subjects during a double-blind clinical trial. In addition, subject safety will be closely monitored and stopping criteria implemented (see Section 5.8).

The PK sampling schedule is considered appropriate given the information available. The rationale for dose selection is discussed in Section 3.2.

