## 8.3.2 Secondary Analysis – ADAS-Cog13 and ERP P300

The separate secondary variables of ADAS-Cog13 and ERP P300 will be analyzed using the same MMRM model that was used for analysis of the primary endpoint.

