#### 6.1 Study Design

This is a Phase 2 multicenter, randomized, double-blind, placebo-controlled, parallel-group, dose ranging study comparing ATH-1017 40 mg/day and ATH-1017 70 mg/day with placebo in subjects with a clinical diagnosis of PDD or DLB (Postuma et al, 2015; Emre, 2007; McKeith, 2017), and with a Montreal Cognitive Assessment (MOCA) score of 11 to 23 at Screening (see Figure 1 for a diagram of the study schema). The study will be conducted at a total of approximately 15 centers in the USA. Subjects and their caregivers will be required to sign an informed consent form (ICF) and will be evaluated against the inclusion/exclusion criteria during a screening period; all eligible subjects will have the option to be tested for glucocerebrosidase (GBA) genotype. Subjects who meet all inclusion/exclusion criteria will undergo baseline ERP P300 assessments at 2 separate baseline visits. At the first baseline assessment (Visit 2a, Prebaseline, Day-10 to Day-3), ERP P300 data shall be uploaded for quality check immediately after completion of the visit. At the second baseline visit (Visit 2b, Baseline, Day 1), no more than 10 days after the Pre-baseline visit, eligible subjects will be randomized in a ratio of 1:1:1 to receive ATH-1017 40 mg/day, ATH-1017 70 mg/day, or placebo. At this Baseline visit (Visit 2b), subjects will undergo pre-dose baseline and post-dose ERP P300.

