#### 9.6 Visit Windows / Unscheduled Visits

Visit windowing will be applied for the analyses which use visit categories. For categorical visit summaries, all visits including early termination assessments and unscheduled visits will be included with the closest scheduled post-baseline visit that includes the efficacy or safety assessment, based on number of days since Day 1. For the primary variable of ERP P300 latency effect, if multiple assessments fall within the same analysis window, pre- and post-dose measurement will be averaged within the analysis window for this variable. For all other efficacy assessments, if multiple efficacy assessments fall within the same analysis window (other than baseline), any non-missing efficacy assessments will be averaged. For all non-efficacy assessments, a last-within-window approach will be used.

The analysis windows for ERP P300, ADAS-Cog13 and COWAT are:

	Protocol-Specified	Analysis-Specified
Analysis Visit	Day	Interval
Week 2	Day 14	Day 2-63
Week 12	Day 84	Day 64-112
Week 20	Day 140	Day 113-161
Week 26	Day 182	Day 162-196
Week 30	Day 210	Day 197-218

The analysis windows for C-SSRS, Physical and Neurological Exams, EG, Vital Signs, Labs are:

	Protocol-Specified	
Analysis Visit	Day	Analysis-Specified Interval
Week 2	Day 14	Day 2-28
Week 6	Day 42	Day 29-63
Week 12	Day 84	Day 64-98
Week 16	Day 112	Day 99-126
Week 20	Day 140	Day 127-161
Week 26	Day 182	Day 162-196
Week 30	Day 210	Day 197-218

The analysis windows for GDS are:

Confidential Page 32 of 57

	Protocol-Specified	
Analysis Visit	Day	Analysis-Specified Interval
Week 12	Day 84	Day 2-133
Week 26	Day 182	Day 134-196
Week 30	Day 210	Day 197-218

The analysis visit windows for MMSE is:

Analysis Visit	Protocol-Specified Day	Analysis-Specified Interval
Week 12	Day 84	Day 2-112
Week 20	Day 140	Day 113-161
Week 26	Day 182	Day 162-218

The analysis windows for MDS-UPDRS, NMSS, ADCS-ADL23, ADCS-CGIC, ADCS-CaGIC, ADCS-CGIS, and PK are:

Analysis Visit	Protocol-Specified Day	Analysis-Specified Interval
Week 12	Day 84	Day 2-133
Week 26	Day 182	Day 134-218

Confidential Page 33 of 57

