- Subject hearing will be tested to establish suitability for ERP assessment (ability to hear or differentiate the 2 different tones necessary for auditory ERP P300 assessment, using the centrally provided ERP equipment); subjects who wear a hearing aid must remove their hearing aid during the Screening auditory test and during ERP P300 recordings.
- o ERP P300 will be performed at the Pre-baseline visit (Visit 2a, Day -10 to Day -3, no dosing); pre-dose and post-dose at Baseline/Day 1 (Visit 2b), Week 2 (Visit 3), Week 12 (Visit 5), and Week 26 (Visit 8). ERP P300 data should be uploaded for quality check immediately after the completion of the Pre-baseline visit (Visit 2a). ERP P300 will also be performed at Safety follow-up (Visit 9, no dosing).
  - Pre-dose ERP P300 assessments will be performed immediately preceding IMP dose but can be up to 1 hour before dose
    in clinic.
  - Post-dose ERP P300 assessments will be performed at approximately 2 (± 1) hours after dose.

Confidential Page 49 of 57

	Subjects who terminate prior to Visit 9 are to complete same assessments as Visit 8/ET (early termination). For clinica outcome assessments, if completed the assessment within 4 weeks of the ET visit they do not need to be repeated; all
	safety outcomes and drug accountability should be performed regardless of interval.
Safety	ADAS-Cog 13 , will be performed pre-dose. For visits after Baseline (except for follow-up when dosing is not applicable), all cognitive assessments will be performed post-dose, in the order of assessments, with ADAS-Cog 13 performed at approximately 1 hour (± 30 minutes) post dose.  C-SSRS and GDS may be completed any time at applicable visits.

Confidential Page 50 of 57

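### SAP 9.2 gives two conflicting baseline rules that both apply to ERP P300 latency, and the last-value rule leaves one of the two pre-dose recordings unused

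*SAP*

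**What the plan says.** SAP 9.2 holds two rules. Its first paragraph repeats protocol 8.2: "For clinical effect measures baseline is defined as the last pre-randomization measurement". Its second paragraph sets aside only the GST score, ADCS-CGI-C and CaGI-C, which are already change scores. It then continues: "For all other efficacy measures, baseline is the average of all measurements prior to first dosing", with a lone value used when only one exists. Neither paragraph is ranked over the other. The protocol has no averaging rule, and SAP Section 8 does not list averaging among the changes from the protocol.

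P300 has two recordings before the first dose. SAP 6.1 says that subjects "will undergo baseline ERP P300 assessments at 2 separate baseline visits". Footnote o of the schedule (protocol Table 1, SAP Appendix 2) places them at Visit 2a, where no dose is given, and at Visit 2b pre-dose. Protocol 3.1 gives the reason for the added recording: it "is intended to reduce possible variability of the baseline measure for this functional variable".

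**The concern.** A programmer following SAP 9.2 literally can compute two different baselines for the same subject. The choice carries into P300 change from baseline, the P300 half of the GST score, and the baseline GST covariate in SAP Appendix 1. If the last-value rule is applied, one of the two recordings does not enter the baseline, contrary to the purpose stated in protocol 3.1.

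The change score is what the retained analysis uses. SAP 10.5 keeps a two-sample t-test on change with no baseline adjustment, so baseline noise passes straight into it. SAP 10.5.1 and 10.5.2 then run the MMRM only if the simple summaries look interesting. An open baseline rule therefore leaves an analyst's choice ahead of a data-dependent decision.

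**Working it through.** **Step 1: do both rules reach P300?**

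- *As a clinical effect measure.* Protocol 8.3 is the section on clinical effect analyses, and within it 8.3.2 says "ERP P300 will be analyzed using the same MMRM model that was used for analysis of the primary endpoint". SAP Table 1 lists P300 latency under the objective on clinical effects.
- *As an efficacy measure.* SAP 6.2.1.3 describes P300 under the efficacy measures heading, and the table of efficacy parameters in SAP Appendix 4 includes "CFB ERP P300 latency".
- *Exemptions.* P300 is not among the three measures that SAP 9.2 sets aside.

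**Step 2: do the rules give different values?** Yes, when both recordings exist. The baselines then differ by half the difference between the recordings. Randomization and the pre-dose recording both fall on Day 1, and the documents do not fix their order. The last pre-randomization value is Visit 2b if the recording comes first and Visit 2a if randomization does. ADAS-Cog13 has one scheduled pre-dose assessment, so it is unaffected.

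**Step 3: is it settled elsewhere?** SAP 9.6 says of P300 that "pre- and post-dose measurement will be averaged within the analysis window for this variable", but its windows start at Day 2 and do not cover baseline.

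**Step 4: size.** The plan has no figure to reproduce: the sample size (75, or 25 per arm) was chosen empirically and no P300 SD or reliability is given. The following are assumptions.

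- Within-subject variance per recording = 1, of which a fraction f (0 to 1) is shared by recordings on the same day.
- The post-baseline value averages pre- and post-dose recordings (SAP 9.6), so its error variance is vp = f + (1−f)/2, from 0.5 to 1.
- Baseline error variance is 1 for the last value and (1+r)/2 for the mean of two days, where r is the error correlation between the two baseline days.
- True-change variance is h, and between-subject variance is b, from 0.5 to 4.

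Formulas:

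- Variance ratio of change, mean versus last value = (vp + h + (1+r)/2) / (vp + h + 1).
- Baseline-adjusted residual variance = b + h + vp − b²/(b + vb), where vb is the baseline error variance.
- SD of one subject's shift between rules = √((1−r)/2).
- SD of the shift in the treatment difference, in standard errors of the last-value difference = √((1−r)/2) / √(vp + h + 1). Arm sizes cancel.

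Worked ends for r = 0:

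- h = 0, f = 0: ratio 1.0/1.5 = 0.667, SD cut 18.4%; shift 0.707/√1.5 = 0.577.
- h = 1, f = 1: ratio 2.5/3 = 0.833, SD cut 8.7%; shift 0.707/√3 = 0.408.

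| r | h | Cut in SD of change | Cut in adjusted residual SD | Shift in treatment difference (SEs) |
|---|---|---|---|---|
| 0 | 0-1 | 8.7-18.4% | 1.8-14.8% | 0.41-0.58 |
| 0 | 2-4 | 4.3-7.4% | 0.8-5.5% | 0.29-0.38 |
| 0.5 | 0-1 | 4.3-8.7% | 0.7-6.7% | 0.29-0.41 |
| 0.5 | 2-4 | 2.1-3.6% | 0.3-2.6% | 0.20-0.27 |

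A simulation at r = 0 with arms of 25 v 50 and 5 v 10 gave shifts of 0.576 and 0.578 (h = 0, f = 0), and 0.407 and 0.408 (h = 1, f = 1), in line with the formula.

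One subject's change moves with an SD of 0.71 within-subject SD (0.50 at r = 0.5). At r = 0 and an assumed within-subject SD of 10, 20 or 30 msec, that is 7.1, 14.1 or 21.2 msec.

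**The case against.** The strongest reply is that the text has one sensible reading. Among the efficacy measures visible in the documents, only P300 has more than one scheduled pre-dose recording, so an averaging sentence that did not govern P300 would change nothing scheduled. The two baseline visits and protocol 3.1 point the same way. That averaging is probably intended stands. But the averaging sentence is not narrower than the last-value sentence, so a specific-over-general reading is not secured by the wording. Even if averaging governs, it departs from protocol 8.2 and SAP Section 8 does not record it.

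A second reply is that P300 is a pharmacodynamic variable (protocol 6.3, SAP 6.2.1.3), while protocol 6.2 on clinical effect variables shows, as published, only ADAS-Cog13. The label is real, but protocol 8.3.2 and SAP Table 1 still place P300 among the clinical effects.

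Three further points stand:

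- Efficacy and biomarker analyses are exploratory (SAP 6), no statistical conclusion may be drawn (SAP 8), and analyses beyond summary statistics are optional (SAP 10.5.6).
- The size rests wholly on assumptions, and the figures are for P300 alone. The GST averages two standardized components. If these are uncorrelated, and ignoring re-standardization, the GST shift is about 1/√2 of the P300 shift: 0.408/1.414 = 0.29 to 0.577/1.414 = 0.41 in the first row of the table, and less with positive correlation.
- Under the last-value rule the Visit 2a recording would still serve the quality check, and could supply the baseline if Visit 2b were missing. It is unused only as a baseline value when both exist.

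**Conclusion.** The concern holds. SAP 9.2 contains two baseline rules that both cover ERP P300 latency and give different numbers, and nothing in the documents says which applies. Averaging is the better supported reading and lowers the noise in an unadjusted change score.

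The gain in the SD of P300 change is 9-18% if errors are independent between days and true change varies no more than the within-subject error. It falls to about 2% if true change varies four times as much and the two baseline errors correlate at 0.5. Under the same two sets of assumptions, switching rules moves the P300 treatment difference with an SD of 0.41-0.58, falling to 0.20, standard errors. The documents cannot narrow these ranges.

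With efficacy exploratory, this is a correction that should be made rather than a threat to the study's conclusions. It affects the P300 and GST summaries, the t-test, and the decision whether to run the MMRM.

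**What to change.** In SAP 9.2, state that the last-pre-randomization sentence does not apply to ERP P300 latency. State that its baseline is the mean of the Visit 2a and Visit 2b pre-dose values, or the single value available, and that this baseline is used for the change scores and for the baseline GST covariate in Appendix 1. The same sentence should say how a recording repeated before dosing counts. Record the choice in SAP Section 8 as a departure from protocol 8.2. ADAS-Cog13 needs no change, and none is proposed for other measures.

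The cost is one or two sentences in 9.2 and one line in Section 8, with no new data or visits. It is best done before the summaries are produced, so that the rule is fixed before anyone judges whether they justify the MMRM.
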